Trial material																		
Drug dispensing		X				X				X		X						
Drug account			X		X					X		X				x		
End-of-Trial															x			

391 \*+/- 3 days. \*\*+/- 7 days. Labs: ^ pregnancy test, ketones, lipid panel^\* and GAD65 (If concern for Type 1 diabetes, GAD65 and ketones  
392 will be ordered during screening, per PI discretion). Pregnancy test for WOCP as deemed by investigator & fasting defined as at least 8  
393 hours without food or drinks or diabetes medications, except water and other prescribed medications.  +/- 7 days, but before  
394 randomization visit. Fasting glucose could be obtained from a chemistry sample obtained during the visit or POC BG. Body  
395 measurement includes: weight, height and waist and hip circumference. @ During "randomization" and "vital signs" visits, subjects will  
396 receive training on device use.

397 **Treatment of subjects:**

398 **Group 1) IDegLira Group**

399 • Discontinue OADs (SU, DPPIVi, glinides, and pioglitazone), except metformin  
400 (unless contraindicated) and SGLT2i.

401 • Start IDegLira at 16 dose steps (degludec 16 units/liraglutide 0.6 mg), per U.S  
402 labeling indications and/or provider discretion.

403 • IDegLira will be given once daily, at the same time of the day with or without food.

404 • IDegLira will be titrated until the maximum dose (50 steps) is reached, up to target fasting  
405 BG between 70 and 100 mg/dl (Treat-To-Target Trial protocol), see algorithm below.

406 • Titration will occur twice a week: 1) self-titration by patients once a week and 2) phone call/  
407 contact by research team once a week, for the initial 8 weeks. After that, patients will self-  
408 titrate study medications per dosing algorithm.

409 • IDegLira will be titrated by 2-step-dose increment (2 IU of degludec and 0.072 of liraglutide),  
410 to a maximum of 8 steps per week.

411 • The maximum allowed dose of IDegLira 50 dose steps provide 50 U of degludec and 1.8mg  
412 of liraglutide.

413 • Titration will be performed twice weekly (every 3 to 4 days) based on the previous self-  
414 monitored fasting (pre-breakfast) BG measurement (mean of 3 consecutive days). Patients  
415 will be provided with self-titration algorithms for insulin adjustments.

416 • Subjects not at goal (fasting or mean SMBG from 3 consecutive days > 300 mg/dl) requiring  
417 > 50 dose steps of IDegLira, will be considered “treatment failures”. Degludec will be added  

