418 to IDegLira as “rescue” basal insulin therapy. The dose of IDegLira will remain unchanged.

419 • The dose of “rescue” Degludec will be recorded and titrated twice weekly to target FPG of  
420 70-100 mg/dl, per provider discretion, as shown below.

Titration algorithm for IDegLira and Degludec pens	Insulin dosage IU/d)*
$\geq 181$	8
141-180	6
121-140	4
101-120	2
71-100	no adjustments
$<70$	-2 If dose $> 45$ U/d, decrease by 10%
$<56$	-4 If dose $> 45$ U/d, decrease by 10%

\* Maximum titration dose per week: 8 units

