#### 528   **Withdrawal Criteria**

530       - The subject may withdraw at will at any time during the trial.  
531       - Pregnancy or intention of becoming pregnant.  
532       - The subject may be withdrawn at the discretion of the investigator due to non-  
533           compliance or due to a safety concern  
534       - The subject will be withdrawn if starting any drugs that interfere with glucose metabolism  
535           (steroids doses equivalent to prednisone > 5 mg/day)  
536       - The subject may be withdrawn if diagnosed with acute pancreatitis (defined as meeting 2  
537           of the following 3 rules: typical abdominal pain, amylase/lipase > 3x UNL and/or  
538           characteristic US, CT or MRI findings)  
539       - If the fasting or mean SMBG during 3 consecutive days is > 300 mg/dl, the investigator  
540           will schedule an unplanned visit as soon as possible, to obtain confirmatory fasting BG  
541           and investigate the cause. If no apparent or intercurrent cause is detected, the patient  
542           may be withdrawn.  
543       - Unable to comply with trial protocol, at investigator discretion.

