#### 544   **Subject Replacement**

546   There will be no replacement of subjects withdrawn after randomization in this trial.  
547  
548

549  
550  
551 **Rationale for Study Population**

552 The target population will include subjects with uncontrolled T2D with HbA1c  $\geq 9\%-15\%$ ,  
553 treated with oral anti-diabetic agents and low dose basal insulin (TDD  $\leq 50$  units/d), in whose  
554 treatment intensification is recommended. Subjects should have been on oral anti-diabetic  
555 agents or basal insulin for at least 90 days (with stable doses of insulin, 10% of dose  
556 fluctuations are acceptable). These subjects need intensification of therapy, and should start  
557 basal insulin and progressively step-up to basal-bolus insulin per national guidelines. However,  
558 these patients may benefit more from a simpler regimen consisting of a single daily injection,  
559 with lower risk of hypoglycaemia and less weight gain, which could improve treatment  
560 adherence. IDegLira is an attractive therapeutic option for these patients for its potency,  
561 flexibility, and potential lower risk of hypoglycaemia and weight gain.

562  
563 **Visit Procedures**

564 Figure 2 and Table 1 provides a description of procedures to be performed at each visit  
565 during the study period. Visits will be distributed as follows: initial/screening visit/CGM baseline  
566 insertion, (visit 1), 2 weeks of screening/run-in period, randomization visit (visit 2), 26-week  
567 treatment period (visits 4-18), and a follow-up safety visit after the end the 26- weeks treatment  
568 period (visit 19). Subjects will have contact with the study team via clinic visits or phone  
569 contacts for a total of 9 clinic visits and 9 telephone contacts. If subjects cannot participate in a  
570 scheduled visit (+/- 3 days), the investigators will arrange for an urgent (as soon as possible)  
571 visit. During follow-up, we will collect the following data (as described in Table 1): glycemic  
572 data, hypoglycemia events, drug compliance, protocol adherence, body measurements, and  
573 adverse events.

574  
575 **Definitions:**

576 • CGM Hypoglycemia: CGM glucose levels  $< 70$ ,  $< 54$ ,  $\leq 40$  mg/dl, with a duration at least  
577 15 minutes by CGM. The end of the event will be when glucose is  $\geq 70$  mg/dl for 15  
578 minutes. A prolonged hypoglycemic event will be defined as CGM levels  $< 54$  mg/dl for  
579 120 minutes or more".

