896       regression to assess other potential confounders. We will perform appropriate model selection  
897       and diagnostic procedures to ensure adequate fit to the data. For outcomes measured at  
898       multiple time points (i.e. longitudinal outcome), we will first conduct cross-sectional analyses as  
899       planned for the non-longitudinal outcomes. Next we will perform repeated measures analyses  
900       that account for with-subject correlations in the longitudinal outcomes. We will analyze  
901       longitudinal continuous outcomes based on repeated measures ANOVA followed by repeated  
902       measures linear regression, and we will analyze longitudinal discrete outcomes by using  
903       repeated measures generalized linear model (GLM). If the assumption of missing completely at  
904       random (MCAR) is reasonable, we shall handle missing data by excluding them from the cross-

905 sectional and the longitudinal data analyses. When MCAR assumption is questionable, we will  
906 assume missing values are missing at random and deal with them by the standard multiple  
907 imputation methods. We plan to conduct statistical analyses using SAS 9.4.

908

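### Patients withdrawn for glucose above 300 mg/dl can drop out of the primary HbA1c test, because no rule puts titration or rescue first and no HbA1c is taken after withdrawal

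*Combined protocol and SAP*

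**What the plan says.** - **Rescue (Treatment of subjects, Group 1).** The rule applies to an IDegLira patient with fasting or mean self-monitored glucose above 300 mg/dl over 3 consecutive days who also needs more than the maximum dose: "> 50 dose steps of IDegLira, will be considered “treatment failures”. Degludec will be added" and then "to IDegLira as “rescue” basal insulin therapy. The dose of IDegLira will remain unchanged". Such a patient stays on study with a week-26 HbA1c due.
- **Withdrawal (Withdrawal Criteria, both arms).** "If the fasting or mean SMBG during 3 consecutive days is > 300 mg/dl, the investigator" arranges an unplanned visit for a confirmatory fasting glucose. The rule goes on: "and investigate the cause. If no apparent or intercurrent cause is detected, the patient" may be withdrawn. It sets no dose condition, does not exempt the titration period, and does not mention rescue.
- **Replacement (Subject Replacement).** "There will be no replacement of subjects withdrawn after randomization in this trial".
- **HbA1c schedule (Table 1).** Weeks -2, 12 and 26 only. There is no early-termination or post-withdrawal sample.
- **Missing data (Statistical Methods).** If missing completely at "random (MCAR) is reasonable, we shall handle missing data by excluding them from the cross"-sectional and longitudinal analyses. If that assumption is doubtful, the analysts will "assume missing values are missing at random and deal with them by the standard multiple" imputation methods. The section names no imputation covariates, no analysis set and no sensitivity analysis, and it does not mention rescue or treatment failure.

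**The concern.** A patient withdrawn under the glucose rule leaves because control is poor, which is close to the primary outcome itself. Dropping such patients, or imputing them from patients who did not fail, flatters whichever arm loses more of them. The decision is discretionary and the trial is open-label, so the investigator knows the arm when choosing between titration, rescue and withdrawal. If IDegLira loses more, the test leans towards non-inferiority. If basal-bolus loses more, it leans the other way. No planned analysis would show either.

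The threshold could be reached here. Entry HbA1c runs to 15%. The fixed bar to randomisation is a glucose above 400 mg/dl, and above 300 mg/dl a repeat test is at the investigator's option. The IDegLira instruction is "Start IDegLira at 16 dose steps (degludec 16 units/liraglutide 0.6 mg), per U.S" labelling or provider discretion, so a patient previously on 50 U of basal insulin may restart at 16. The same patient on basal-bolus starts degludec at 40 to 50 U with no cap. For insulin-naive patients the starting doses are closer.

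**Working it through.** **1. The plan's own figure.** Inputs from Sample Size Calculation: margin 0.4, SD 0.85, true difference 0, one-sided alpha 0.05, 57 per arm. The non-central t power is 80.3% at 57 per arm, so the stated 80% reproduces. Recruiting 75 and losing 20% leaves 75 × 0.8 = 60 per arm, with power 82%. I use 60 below.

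**2. The two rules side by side.**
- At the 50-step cap, an IDegLira patient above 300 mg/dl meets both rules. One says degludec is added; the other permits withdrawal. No text ranks them.
- Below the cap, only the withdrawal rule applies. From 16 steps at no more than 8 a week, the cap is reached after (50 − 16)/8 = 4.25 weeks at the earliest.
- A patient withdrawn before week 12 has no on-treatment HbA1c. Self-monitored glucose exists, and fasting glucose is due at weeks 4 and 8.

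**3. Effect of excluding such patients.** Assumptions, none from the documents: the true difference is exactly 0.4 when every week-26 value counts; the k IDegLira patients with the worst trigger glucose are withdrawn; trigger glucose has correlation r with HbA1c change. Shift in the estimated difference = (k/60) × (excess of excluded patients over the rest). At r = 0.7 the excess is 1.40, 1.25 and 1.13 points for k = 1, 3, 6:
- k = 1: 1.40/60 = 0.023, difference 0.377
- k = 3: 3 × 1.25/60 = 0.0625, difference 0.338
- k = 6: 6 × 1.13/60 = 0.113, difference 0.287

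Hand check for k = 3: SE = 0.85 × √(1/57 + 1/60) = 0.157; 0.0625/0.157 = 0.40; 1 − Φ(1.66 − 0.40) ≈ 10.4%. Simulation gives slightly more because trimming also narrows the SD.

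Simulated chance of declaring non-inferiority (100,000 trials per cell, pooled t-test, nominal 5%):

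| r | k = 1 | k = 3 | k = 6 |
|---|---|---|---|
| 0.7 | 6.8% | 11.1% | 18.4% |
| 0.5 | 6.3% | 8.9% | 13.2% |
| 0.2 | about 5% | about 6% | about 7% |
| 0 | 5% | 5% | 5% |
| −0.3 | below 5% | 3.5% | 2.6% |

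**4. Losses in both arms or the other arm (r = 0.7).** Losses of 3 v 3 give 5.6%; 6 v 3 (IDegLira v basal-bolus) gives 10.5%. If basal-bolus alone loses 3 and the true difference is 0, power falls from 82% to about 70%.

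**5. Imputation instead of exclusion (r = 0.7; k = 3 and 6).**
- No on-treatment data in the model: 11.1% and 18.7%.
- Week-12 HbA1c in the model (assumed correlation 0.7 with week 26): 8.0% and 11.0%.
- Trigger glucose in the model: about 5% for both (4.9% to 5.6% across runs).

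**6. Tipping point.** With an observed difference of 0 and 60 per arm, the upper limit is 1.658 × 0.85 × √(2/60) = 0.257. To reach 0.4, 3 imputed IDegLira patients would each have to be (0.4 − 0.257)/(3/60) = 2.9 points worse than analysed; 6 would each have to be 1.4 points worse.

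**The case against.** The strongest reply is that the rules fit together on an ordinary reading. Rescue is specific and mandatory, and needs more than 50 steps as well as the glucose value. Withdrawal is general and permissive, and follows a visit, a confirmatory test and a search for a cause. Unfinished titration, or the dose cap, is itself an apparent cause. In addition, insulin may be started or raised in run-in for glucose above 300 mg/dl, a value above 300 mg/dl can itself lead to screen failure, and both arms have weekly contact and twice-weekly titration for 8 weeks. Few patients may be affected.

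On the analysis side, the missing-data rule allows exclusion only where missing completely at random is reasonable. It plainly is not for these patients, so the wording points to imputation, and imputation that includes the glucose data removes the bias in this model. The correlation with change in HbA1c is also unknown. Patients above 300 mg/dl may have the highest baseline values and the most room to fall.

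Most of this stands, and it limits the size of the point. What remains is that the order of the rules is not written down, the choice of missing-data route has no criterion, no imputation covariates are named, and the week-26 value is never collected.

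A reader might also infer that keeping rescued patients in the comparison invalidates it. The documents do not support that. Using HbA1c after rescue is a valid treatment-policy analysis and only needs stating.

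**Conclusion.** The gap is real and worth closing: discretionary, outcome-related withdrawal without later HbA1c can remove patients from the primary non-inferiority test. Its size and direction cannot be established, because the documents give no rate of rescue or glucose withdrawal and no correlation with HbA1c change. With 1 loss in 60 the effect is small. With 3 to 6 one-sided exclusions and a strong correlation, the error rate reaches about 11% to 18%. With a weak correlation, balanced losses or imputation using the glucose data, it stays near 5% (at most about 7%).

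A reader might infer that the plan is biased in favour of IDegLira. The lower starting dose and the cap make more IDegLira triggers plausible in patients already on basal insulin, but the withdrawal rule covers both arms, and losses confined to basal-bolus would work against IDegLira. A reader might also infer that one trigger always gives contradictory instructions. Rescue needs the extra dose condition, so the direct collision is confined to IDegLira patients at the cap. This is a cheap improvement to make, not a defect that overturns the design.

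**What to change.** 1. **Withdrawal Criteria.** State that titration to 50 steps and then rescue degludec (IDegLira), or further titration (basal-bolus), come before withdrawal on the glucose rule. Keep the investigator's freedom to stop study drug for safety.
2. **Follow-up.** In both arms, a patient stopped on the glucose rule stops study drug only and still has the week-26 HbA1c unless consent is withdrawn. Use that value in the primary analysis, and state that values after rescue are used too.
3. **Statistical Methods.** Never treat a missing week-26 HbA1c after a glucose-rule stop as missing completely at random. Impute it with self-monitored glucose, fasting glucose and any week-12 HbA1c in the model, and show a tipping-point result beside the primary, not as a second hurdle.
4. **Reporting.** Give rescues, glucose-rule stops and therapy after stopping, by arm.

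Cost: wording, plus one HbA1c visit per stopped patient, which some will decline. Power with all 60 values per arm at SD 0.85 stays at 82%, though keeping failures may raise the SD somewhat. There is one real drawback: usual care after stopping may be basal-bolus, the comparator, which can pull the arms together and so towards non-inferiority. A supportive analysis that imputes values after stopping should therefore accompany the primary.

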#### Group 2: Basal-Bolus Insulin Group (Begin BB trial)

- Discontinue OADs (SU, DPPIVi, glinides, and pioglitazone), except metformin (unless contraindicated) and SGLT2i.
- Insulin naïve participants will start at a daily dose of 10 units of degludec U-100 (or 0.2 u/kg/d per investigator discretion).
- Participants previously using basal insulin [neutral protamine hagedorn (NPH), mixed insulin, detemir or glargine U100] will be switched to study-provided degludec pens.
- For participants taking basal insulin prior to randomization, the conversion dose is 1:1 unit. The total daily basal dose could be the same or reduced by 20% at the investigator's discretion.
- Titration will be performed twice weekly based on the previous self-monitored fasting (pre-breakfast) BG measurement (mean of 3 consecutive days). Titration will occur as follows: 1) self-titration by patients once a week and 2) phone call/ contact by research team once a week, for the initial 8 weeks. After that, patients will self-titrate study medications per dosing algorithm.
- Degludec will be given once daily at the same time, and titrate up to fasting blood glucose 70-100 mg, with no maximum dose.
- Basal insulin should be adjusted before adjusting pre-meal aspart, as shown below.

448 **Degludec U100 Insulin adjustment**

449

Mean fasting BG from preceding 3 days (mg/dl)	Insulin dosage IU/d)
>181	8
141-180	6
121-140	4
101-120	2
71-100	no adjustments
<70	-2 If dose > 45 U/d, decrease by 5%
<56	-4 If dose > 45 U/d, decrease by 10%

450

451

452 **Aspart Insulin dosage:**

453 • Aspart will be given before meals, to target pre-meal BG < 70-100 mg/dl.

454 • At the start of the trial, participants will be prescribed 4 U insulin aspart before the  
455 largest/main meal or; before each main meal (3 typical large meals per day:  
456 breakfast, lunch, and dinner,  $\leq$ 4 times per day) per investigator discretion.

457 • For insulin naïve participants or per investigator discretion, total aspart dose will  
458 calculated at 0.2 u/kg/d, and equally divided in three doses to be started before the  
459 main/largest meal or before each meal (3 typical large meals per day: breakfast,  
460 lunch, and dinner,  $\leq$ 4 times per day), per investigator discretion.

461 • If patients are started on only one dose for the largest meal, a second and third dose  
462 may be added, as detailed above. Subjects will be provided with titration algorithms.

463 • The dose adjustment of insulin aspart will be based on the pre-prandial BG of the  
464 subsequent meal or bedtime BG (i.e. the pre-dinner value will be based on the  
465 bedtime BG), per provider discretion, as shown below:

Pre-prandial and bedtime BG (mean BG from preceding 3 days), mg/dl	Aspart dosage IU/d)
>181	+4
141-180	+3
101-140	+2
71-100	no adjustments
<70	-2
<56	-4

475

476

477 **Study population:**

478 A total of 150 subjects (75 subjects in each arm) will be included in the study (screening  
479 about 300), randomized in a 1:1 manner, and started on study medications (as show in Fig 2).  
480 Based on an anticipated screening failure rate of 40% and an attrition rate of 20%, total of 300  
481 patients will be screened. The study will be conducted at Emory University Hospital Midtown  
482 and Grady Hospital in Atlanta, Ga and second site TBA

483  
484 **Inclusion Criteria**

485 1. Males or females between the ages of 18 to 80 years  
486 2. Type 2 diabetes, diagnosed for  $\geq$  6 months  
487 3. HbA1c  $\geq$  9% - 15%  
488 4. Previously treated with oral antidiabetic agents, including metformin, sulfonylurea,  
489 repaglinide/nateglinide, pioglitazone, DPP4 inhibitors, SGLT2 inhibitors, (monotherapy +  
490 basal insulin) or in combination therapy (2-3 agents), and/or on basal insulin (neutral  
491 protamine hagedorn (NPH), mixed insulin, detemir or glargine U100) at a total daily dose  
492 (TDD)  $\leq$  50 units (stable doses of basal insulin for at least 90 days, defined as up to  $\pm$ 10%  
493 variability)  
494 5. BMI  $\leq$  45 Kg/m^2

495  
496

497 **Exclusion Criteria**

498 1. Age  $<$  18 or  $>$  80 years  
499 2. Subjects with type 1 diabetes or LADA: positive GAD-65 antibody and/or ketones  
500 3. Subjects with a BG  $>$  400 mg/dL during the screening visit and laboratory evidence of diabetic  
501 ketoacidosis  
502 4. Previous treatment with GLP-1 agonists (during prior 3 months)  
503 5. Previous treatment with basal-bolus insulin (within prior 3 months, except transient treatment  
504 with during hospital admission)  
505 6. Recurrent severe hypoglycemia or known hypoglycemia unawareness.  
506 7. Personal or family history of medullary thyroid cancer or multiple endocrine neoplasia 2  
507 8. Patients with acute or chronic pancreatitis, pancreatic cancer  
508 9. Patients with clinically significant hepatic disease (cirrhosis, jaundice, end-stage liver  
509 disease) or significantly impaired renal function (GFR  $<$  30 ml/min).  
510 10. Treatment with oral or injectable corticosteroid (equivalent or higher than prednisone 5  
511 mg/day), parenteral nutrition and immunosuppressive treatment.  
512 11. Mental condition rendering the subject unable to understand the nature, scope, and possible

513           consequences of the study  
514   12. Hypersensitivity to study drugs  
515   13. Participating in another investigational drug trial  
516   14. The receipt of any investigational drug (within 3 months) prior to this trial.  
517   14. Previously randomized in this trial  
518   15. Heart Failure NYHA class 4 or uncontrolled hypertension (blood pressure > 180/110  
519           mmHg)  
520   16. Female subjects who are pregnant or breast-feeding at time of enrollment into the study  
521   17. Females of childbearing potential who are not using adequate contraceptive methods (as  
522           required by local law or practice)  
523   18. Known or suspected allergy to trial medications (degludec, liraglutide, aspart), excipients, or  
524           related products.  
525   19. Subjects could be excluded based on PI's discretion  
526   20. Unable to comply with trial protocol, and/or at investigator discretion  
527   21. Patients receiving treatment for active diabetic retinopathy or with proliferative retinopathy

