271                   (responder’s rate)
- 272                   • Percent of patients reaching A1c  $< 7.5\%$  without weight gain and no hypoglycemia”
- 273                   • Percent of patients with A1c  $> 10\%$  and  $> 11\%$  that achieve A1c  $< 7.5\%$  and  $< 8\%$

- Percent of patients with HbA1c <7.0% at 26 weeks and no weight gain
- Percent of patients with HbA1c <7.0% at 12 weeks and no hypoglycemia
- Incidence of documented symptomatic hypoglycaemia, defined as an event with typical symptoms of hypoglycaemia accompanied by SMBG or CGM (<70 mg/dL and < 54 mg/dL) that occurs at any time of the day
- Incidence of asymptomatic hypoglycaemia, defined as no typical symptoms reported by the subject but detected by SMBG or CGM (<70 mg/dL and < 54 mg/dL)
- Incidence of severe hypoglycaemia, defined as severe cognitive impairment requiring assistance from another person
- Incidence of nocturnal symptomatic hypoglycaemia, defined as an event with typical symptoms of hypoglycaemia accompanied by SMBG or CGM <70 mg/dL and < 54 mg/dL that occurs between 00:00 and 05:59 hrs
- Incidence of nocturnal asymptomatic hypoglycaemia, defined as SMBG or CGM <70 mg/dL and < 54 mg/dl between 00:00 and 05:59 hrs
- Percentage of time below 70 mg/dL and <54 mg/dl as obtained by CGM
- Percentage of time in range (BG 70-180) as measured by CGM
- Glycemic variability, as measured by SD (standard deviation), %CV (coefficient of variance), Mean Amplitude Glucose Excursions (MAGE)
- Patient satisfaction and quality of life, as measured by the DTSQ and T R I M - D questionnaires
- Number of emergency room visits and hospital readmissions
- Change from baseline in total insulin dose (units/day)
- Number of treatment emergent AE

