672 Metformin dose will be titrated up to 1000mg twice daily or to the maximum tolerated  
673 dose, unless contraindicated, per investigator's discretion.
- 674 • Basal Insulin therapy [NPH, mixed insulin, or basal insulin (glargine U100, detemir)] at  
675 TDD ≤50 units will continue at same insulin dosage until randomization. Insulin can be  
676 initiated, or dose could be increased during run-in period in those subjects with severe  
677 hyperglycemia (BG>300 mg/dL) and/or glucotoxicity per investigator's discretion, for  
678 subject's safety reasons.
- 679 • Patients will be instructed in performing glucose testing at home before meals, with a  
680 minimum of 2 out of the 4 pre-meal and/or bedtime glucose measurements per day.
- 681 • Patient not randomized in the trial will be considered screening failures, and no data will  
682 be collected since these patients will not receive study medication.

683

684

685

686 Preparation for Visit 2 (Randomization visit)

- 687 • Patient will be instructed to complete the 8-point SMBG, and to titrate up metformin,  
688 unless contraindicated.
- 689 • All patients will be instructed to provide daily glucose records. In addition, they will

690                   perform an 8-point SMBG done prior to Visit 3 (as described above).

691     • Patients who complied with the 8-point glucose testing (up to 6 points) and fulfill the

692                   eligibility criteria at Visit 2 will be randomized to participate in the study.

693     • Reminder to bring CGM sensor for collect and download.

694

695

696     **Randomization (Visit 2, Week 0)**

697     • Patients will be randomized to each treatment group

698     • Continue metformin therapy at same dose, unless contraindicated or for safety issues

699     • Discontinue other OADs and insulin formulation

700     • If BG > 400 mg/dl, patients will not be randomized, and considered screening failures.

701     • If BG > 300 mg/dl, investigator may order a confirmatory glucose test (at a different time)

702                   before considering the subject screen failure.

703     • Subjects will receive detailed instruction on the use of the IDegLira pen or IDeg and

704                   Aspart Pens and the titration algorithm.

705     • Patient will receive study medications. Subjects randomized to IDegLira will be

706                   instructed to not exceed 50 dose steps and to notify investigators if needed.

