940 will also be available at all times to answer questions that participants may have during the  
941 consent procedure or during the time a participant is enrolled in the study. The consent form  
942 will be completed in accordance with the IRB guidelines of Emory University. A signed copy of  
943 the consent form will be provided to the participant and a copy will be placed in the file that is  
944 maintained for each participant in the study office.

945 Informed consent will follow the procedure of Emory University Institutional Review  
946 Board. Every potential participant will be informed in writing and verbally with the important and  
947 key points of the study. One of the investigators or research coordinators will obtain an  
948 informed consent prior to inclusion of a patient into the study.

949 The study will be conducted in accordance with the Declaration of Helsinki and will be  
950 conducted in accordance with the ICH GCP guidelines. The sponsor-investigator will comply  
951 with all applicable regulatory and legal requirements, ICH GCP guidelines and the Declaration  
952 of Helsinki in obtaining and documenting the informed consent.

953

954 **STUDY SCHEDULE:**

955 The study will be conducted at two sites: at 1) Emory University Hospital Midtown and  
956 Grady Memorial Hospital in Atlanta, GA; and at 2) TBA. An additional site will be considered if  
957 funds are available.

958 Based on our prior trials experience, we anticipate 3-4 potential candidates per week,  
959 including the collaborating institutions, for a total recruitment period of approximately 12  
960 months. Since the study requires a 6-month follow up period, we anticipate a study length of  
961 18-24 months.

First subject in	2019 January
Screening	~300
Randomized	150
Last subject recruited	2020 June/July
Last subject in (completed)	2021 Nov/Dec
Data analysis	2021 DEC
Submission to congress or journal	ADA 2021, Major journal and/or Diabetes Care 2021

962

963 **Study DRUGS and materials:**

964 **Study medication(s) / devices(s)**

965 • Group 1: IDegLira pens will be supplied by the sponsor and given free of charge to the study  
966 subjects. IDegLira is a FRC agent, including basal insulin degludec and GLP-1 agonist

967 liraglutide. The starting dose of IDegLira is at 16 dose steps (degludec 16 units/liraglutide  
968 0.6 mg). The maximum allowed dose of IDegLira 50 dose steps provide 50 U of  
969 degludec and 1.8mg of liraglutide.

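### The total-insulin-dose outcome does not say which dose is baseline; define it as the last pre-randomisation dose and adjust for it

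*Combined protocol and SAP*

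**What the plan says.** The secondary outcomes under ENDPOINTS include "Change from baseline in total insulin dose (units/day"). The entry names no baseline visit, no source for the baseline dose and no end time point.

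Statistical Methods sends continuous secondary outcomes measured at one time point through the same strategy as the primary outcome: Wilcoxon and t-tests between the groups. It then mentions variable selection towards a final model but names no covariate.

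The starting doses are as follows.

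- **IDegLira (Group 1):** "Start IDegLira at 16 dose steps (degludec 16 units/liraglutide 0.6 mg), per U.S" "labeling indications and/or provider discretion". The section on study drugs and materials repeats the 16 dose steps without the discretion clause.
- **Basal-bolus (Group 2), prior basal insulin:** "For participants taking basal insulin prior to randomization, the conversion dose is 1:1 unit". Then: "The total daily basal dose could be the same or reduced by 20% at the investigator's discretion".
- **Basal-bolus, no prior insulin:** "Insulin naïve participants will start at a daily dose of 10 units of degludec U-100 (or 0.2 u/kg/d per investigator discretion").
- **Aspart (basal-bolus only):** 4 units before the largest meal or before each main meal, or 0.2 u/kg/d in total for insulin-naive participants or at the investigator's discretion.

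Under Instructions for Run-In Period, prior insulin generally continues unchanged until randomisation, but it may be "initiated, or dose could be increased during run-in period in those subjects with severe" hyperglycaemia or glucotoxicity.

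**The concern.** A change score compares arms fairly only if the subtracted value could not have been influenced by the assignment. The last insulin dose before randomisation meets that condition. The first study dose does not: it is chosen after randomisation, by a rule that differs between arms. An analyst who took the week-0 study dose as baseline would remove part of the treatment difference that the outcome is meant to measure.

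The trial is open-label and the term is undefined, so the choice could be made after doses are known. At stake is the size, and possibly the direction, of the statement about which regimen needs more insulin.

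**Working it through.** The documents give no figure for this outcome, so there is none to reproduce. The primary sample size does reproduce: 2 × (1.645 + 0.842)² × 0.85² / 0.4² = 55.8, so 56 per group by the normal approximation. With the t-test, 57 per group gives 80.3% power. Nothing below affects it.

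**1. Identity.** Let D be the difference (basal-bolus minus IDegLira) in mean end-of-treatment dose, and G the same difference in the value subtracted. The difference in change is D − G. The comparison is undistorted if G is zero in expectation.

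**2. G if the week-0 study dose is subtracted.** G = basal-bolus start − 16. The IDegLira start is taken at its default. Prior doses run from 0 to 50 units/day under the entry criteria. Except in the weight-based rows, aspart is 4 units (one meal) or 3 × 4 = 12 units (three meals). Body weights are assumed.

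| Prior insulin (units/day) | Lowest start | Highest start | G |
|---|---|---|---|
| 10 | 0.8 × 10 + 4 = 12 | 10 + 12 = 22 | −4 to +6 |
| 30 | 0.8 × 30 + 4 = 28 | 30 + 12 = 42 | +12 to +26 |
| 40 | 0.8 × 40 + 4 = 36 | 40 + 12 = 52 | +20 to +36 |
| 50 | 0.8 × 50 + 4 = 44 | 50 + 12 = 62 | +28 to +46 |
| None, fixed starts | 10 + 4 = 14 | 10 + 12 = 22 | −2 to +6 |
| None, 10 units basal, aspart 0.2 u/kg, 70 to 110 kg | 10 + 14 = 24 | 10 + 22 = 32 | +8 to +16 |
| None, both 0.2 u/kg, 70 to 110 kg | 0.4 × 70 = 28 | 0.4 × 110 = 44 | +12 to +28 |

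Weight-based aspart for a prior user would widen the range: at 50 units, 1:1 and 90 kg, 50 + 18 − 16 = 52.

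**3. Consequence for an assumed D of 20 units/day.**

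- All on 30 units before the trial, converted 1:1 plus 12 aspart: 20 − 26 = −6 (reversed).
- Half of them naive at 10 + 4: G = 0.5 × (−2) + 0.5 × 26 = 12, so 20 − 12 = +8 (shrunk).
- All naive at 10 + 4: 20 − (−2) = +22 (slightly enlarged).

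**4. Pre-randomisation baseline.** Randomisation makes G zero in expectation, so the difference in change is D. A simulation checked this with 75 per arm and 4,000 runs. Its assumptions were: half naive; the others uniform on 10 to 50 units; basal-bolus start 10 or the prior dose, plus 12 aspart; every IDegLira start 16; end dose 20 + 0.5 × prior dose with residual SD 15; D = 20. The mean differences were 20.0 with the pre-randomisation baseline, 20.1 for end dose alone and 4.1 with the week-0 study dose subtracted. The last agrees with the identity: G = 0.5 × 10 + 0.5 × 30 + 12 − 16 = 16, and 20 − 16 = 4.

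**5. Precision.** Under the same assumptions the prior dose has mean 15 and variance 0.5 × (30² + 40²/12) − 15² = 291.7. End dose has variance 0.5² × 291.7 + 15² = 297.9. Change from the prior dose has slope 0.5 − 1 = −0.5 on it, hence the same variance. Adjusting for the prior dose leaves 225, a ratio of 225/297.9 = 0.76. The gain depends on the assumed slope.

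**The case against.** A reader might infer that the plan does subtract the week-0 study dose, so that the comparison is biased as written. The documents do not support this. No section says so, and most uses of the term point to data collected before study drug. The visit-1 CGM is described as baseline information collected before drug exposure. The data-handling section counts diabetes treatment history among baseline data. Table 1 schedules no HbA1c between week −2 and week 12. Prior insulin generally runs until randomisation, so a pre-randomisation dose exists. This part of the objection stands.

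It does not close the question. Other Assessments gives TRIM-D at baseline, and Table 1 places its first administration at week 0, the visit at which study drug is supplied. A week-0 reading is therefore available within the protocol's own usage.

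Three other stronger readings also fail.

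- **IDegLira always starts at 16 whatever the earlier dose.** Group 1 allows provider discretion. The study-drugs section omits that clause, and the two statements should be reconciled; 16 is only the default used in this calculation.
- **Run-in changes bias the comparison.** They occur before randomisation, so they cannot create a systematic difference by arm. They only leave open which pre-randomisation value to use.
- **The outcome carries the claim of a simpler regimen.** The protocol rests that claim on once-daily injection, satisfaction and adherence. Insulin dose is one item in an unranked list.

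It is also fair to say that, once baseline is the pre-randomisation dose and is a covariate, change and final dose give the same treatment estimate. Analysing final dose is then a matter of clarity, although it removes any temptation to subtract a study dose.

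**Conclusion.** The baseline for this outcome is undefined, and the one comparison specified for it is unadjusted. Both are worth correcting, at minor severity.

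The distortion is conditional on the week-0 study dose being used as baseline. It would then be large for participants near the entry ceiling for prior insulin and small, or in the other direction, for those on low prior doses or naive participants on fixed starts. Its average cannot be stated, because the documents do not give the share of naive participants, the distribution of prior doses or the body weights. The reversal shown above also depends on an assumed end-of-treatment difference, so it shows what could happen and does not predict the trial's result. Under a pre-randomisation baseline there is no such bias, and the remaining gain is precision.

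**What to change.** In the outcome list and Statistical Methods, state three things.

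1. Baseline is the last total daily insulin dose before randomisation, 0 if the participant was taking none. Insulin started or changed in the run-in counts towards it.
2. The outcome is total daily insulin dose at week 26: IDegLira units plus any rescue degludec in one arm, degludec plus aspart in the other.
3. The arms are compared by a linear model with treatment and that baseline as covariate. The study-drug starting dose is not subtracted. If a change score is still wanted for presentation, it is taken from the same pre-randomisation dose.

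The cost is a line or two of wording. Current medications are documented at screening, diaries record insulin doses from then on, and rescue degludec is recorded; the team need only confirm that the last pre-randomisation dose reaches the database. No visit, sample size or dosing rule changes.
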